9.1.1. Participant interviews

At the point of group allocation, a sub-sample of participants from the intervention group (n=8) and the control group (n=8) will be randomly selected for interviews. Interviews will be held 1-3 days after completion of the intervention in a private clinical room (30-45 minutes).

Using an intention-to-treat approach, individuals who drop out of the intervention will be asked to participate in an interview. Based on the positive feedback from our ongoing preliminary trial and our PPI events, we anticipate a low dropout rate. For this reason, all participants whom drop out will be asked to partake in an interview (non-randomly) to ensure that key information is not missed.

Participant interviews will focus on:

- Exercise equipment: comfort and ease of use.
- Exercise components: mode, duration, intensity and frequency.
- Perceived effectiveness of the intervention.
- Intervention-related burden on participant.
- Exercise self-efficacy, motivation and optimism.
- Acceptability of the study procedures.

At the 3-month follow-up appointment, a brief semi-structured interview (15-20 minutes) will be conducted with the same participants that were interviewed during their hospital stay (n=16) to gather information regarding the impact of hospital-based stroke rehabilitation on lasting exercise-related self-efficacy, motivation, optimism and emotional wellbeing.

9.1.2. Healthcare professional interviews

After the final participant has completed the trial, we aim to interview healthcare professionals to understand the retrospective acceptability of the study procedures and what impact the research had on clinical practice. We will recruit a convenience sample of 3-5 healthcare professionals. We aim to select a range of practitioners from different disciplines with different levels of seniority. Each interview is estimated to last for up to 30 minutes.

Healthcare professional interviews will focus on:

- Attitude towards the intervention.
- Intervention-related burden on staff and participants.
- Perceived effectiveness of the intervention.

9.2. Justification of investigations and outcome measures

The proposed study activities, investigations and outcome measures aim to achieve a balance between scientific rigour, practicality and patient burden. Where possible, routine measures will be utilised to prevent duplication of work and to reduce patient burden. We acknowledge that the timing of routine assessments may vary depending on staff workload and patients' health. If relevant assessments are missed or significantly delayed, where appropriate, the research team will conduct them. Follow-up assessments will be conducted at a 3-month follow-up appointment with the Study Doctor.

Table 4. Justification of investigations and outcome measures

Domain	Outcome measure	Justification
Demographic	Age, sex and ethnicity	Description of demographic data will improve the generalisability of this work and may help us to identify demographic trends which otherwise may be masked by inclusion within a larger, more diverse group.
Diagnostic	Time since stroke	Careful attention must be paid to the timing of the intervention relative to stroke onset . Distinct biological events occur within the first week of stroke. Intervening too early may exacerbate health, whereas intervening too late may miss a 'window of neuroplasticity' (see section 4, Rationale).
	Stroke aetiology	This research builds on promising findings from pre-clinical studies utilising rodent models of ischaemic stroke . The effects of aerobic exercise early after haemorrhagic stroke are less clear. Patients with haemorrhagic stroke will be therefore excluded from the study.
Pharmacological	Use of medications which modify haemodynamics and psychoemotional state	It is important to know if medications are likely to affect other outcome measures. For example, beta-blockers lower heart rate and blood pressure. The recommended method of prescribing exercise intensity relies on the estimation of peak

		heart rate (62). Without knowledge of beta-blocker use, there would be uncertainty around what exercise intensity an individual is exercising at. Further, beta-blockers reduce resting heart rate which may cause side effects including fatigue and dizziness (73). This may adversely affect exercise performance, fatigue, mood, cognition and HRQoL.
Disability	The National Institutes of Health Stroke Scale (NIHSS) (74)	The NIHSS is a clinical measure of neurological disability which is routinely used in stroke medicine. We will use baseline NIHSS score to stratify participants into two subgroups: 1) minor to moderate stroke (NIHSS: ≤ 15), and 2) moderate to severe stroke (NIHSS: > 15). Stratification by NIHSS score will ensure that each study arm contains an even balance of participants from across the stroke severity spectrum.
	Modified Rankin Scale (mRS) (75)	The mRS is a questionnaire-based measure of stroke-induced disability which is commonly used in stroke research. We will use the mRS to assess the trajectory of stroke recovery. Using the mRS will enable follow-on research to be included in meta-analyses. *The mRS is routinely used in the STH NHS acute stroke service.
Cardiovascular risk	Body mass index, cholesterol/HDL ratio, systolic blood pressure, smoking status, demographics, comorbidities	It is of interest to understand how baseline cardiovascular risk factors relate to the incidence of cardiovascular events (e.g. stroke recurrence) throughout the study (76). *Cardiovascular risk factors are routinely measured in clinical practice, therefore no additional assessments will be undertaken by the research team.
Length of hospital stay	Number of days spent in hospital	Length of stay (LoS) is a key NHS quality indicator. Longer LoS is associated with poorer medical outcomes and greater financial costs (77). Aerobic exercise may influence stroke recovery trajectory and thereby LoS.
Psychoemotional state		
Health-related quality of life	EuroQol Quality of Life Index (EQ-5D) (78)	Health-related quality of life (HRQoL) and mood can be adversely affected after stroke (4,81,82). Exercise interventions improve mood and HRQoL (81,83). Measuring EQ-5D, PHQ-9 and GAD-7 will enable the assessment of the effects of the intervention on HRQoL and mood.
Depression	Patient Health Questionnaire (PHQ-9) (79)	
Anxiety	Generalised Anxiety Disorder (GAD-7) (80)	*PHQ-9 and GAD-7 are the only routine psychoemotional assessments used in the STH NHS acute stroke service.

Optimism	Revised Life Orientation Test (rLOT) (84)	A higher level of optimism is associated with lower levels of inflammation and better health outcomes across a number of health conditions (85). An optimistic outlook may mitigate inflammation and in turn contribute to a better recovery after stroke. It is of interest to understand how the level of optimism at baseline may contribute to health outcomes. In addition, it is of interest to assess how the intervention may alter optimism. *Optimism is not routinely measured in the STH NHS acute stroke service.
Exercise self-efficacy	Short Self-Efficacy for Exercise scale (86)	Self-efficacy plays an influential role in the adoption and maintenance of exercise behaviour in older adults (87). Those with higher levels of exercise self-efficacy are better equipped to overcome barriers to exercise compared to those with low self-efficacy. Initiating an aerobic exercise intervention during the early stage of stroke rehabilitation may enhance self-efficacy and result in higher levels of participation in exercise. *Self-efficacy is not routinely measured in the STH NHS acute stroke service.
Fatigue & perceived exertion	Fatigue Severity Scale (FSS) (88)	Post-stroke fatigue is a common, debilitating complication of stroke (91). The management and prevention of post-stroke fatigue was ranked 6 th in the top 10 research priorities relating to life after stroke (agreed by stroke survivors, caregivers, and health professionals)(92). There is limited evidence regarding the effects of exercise interventions on post-stroke fatigue (93). Measuring this outcome using the FSS will help develop the evidence base.
	Rating of Fatigue Scale (RoFS) (89)	The RoFS will enable us to understand transient (acute) fatigue as opposed to generalised chronic fatigue. This is relevant because a patient may partake in various therapies and assessments throughout each day (differing in intensity and duration) which may adversely affect their performance during a subsequent therapy or assessment.
	Rating of perceived exertion (RPE) (90)	RPE is a subjective measure of exercise difficulty , from the participant's perspective. We will utilise the RPE scale to guide exercise workload during each exercise session. RoFS and RPE are not routinely used in the STH NHS acute stroke service. FSS, is routinely used.
Cognitive function	Montreal Cognitive Assessment (MoCA) (94)	Improvement of post-stroke cognition was ranked 1 st amongst the top 10 research priorities relating to life after stroke (92). Aerobic exercise has positive effects on cognitive function after stroke (95). The MoCA is a simple assessment which will

		
help elucidate the impact of the intervention on cognitive function.
 
*The MoCA is routinely used in the STH NHS acute stroke service.

Quadricep muscle morphology	
Muscle ultrasound (96,97):
 
Rectus femoris cross sectional area and muscle thickness.
 
Vastus lateralis muscle thickness and angle of pennation.
	
Acute stroke patients spend 98% of their time physically inactive (52). Sedentary behaviour during hospitalisation causes accelerated muscle atrophy. This increases the risk of sarcopenia, disability and stroke recurrence (98,99). This issue is particularly important in stroke where recovery of motor function is dependent on intensity of rehabilitation, and fitness level represents a 'neurorehabilitation ceiling' (26). In non-ambulatory acute stroke patients, a single week of immobility leads to 12.8% and 9.3% reductions in quadricep muscle thickness in the paretic and non-paretic limbs, respectively (100). Aerobic exercise may mitigate muscle atrophy therefore measurement of muscle morphology is of interest.
 
Hypoallergenic ultrasound gel and nitrile gloves will be used. If a patient has a known allergy to ultrasound gel, this test will be excluded.
 
*Muscle ultrasound is not routinely used in the STH NHS acute stroke service.

Physical activity	
Accelerometers
 
Global Physical Activity Questionnaire (GPAQ) (101)
	
Total physical activity (i.e. rehabilitation) dose moderates change in motor function and level of disability (102). We will use therapist medical notes to quantify usual care therapy dose. However, patients only spend a minor proportion of their time with therapists. We will quantify physical activity levels for the remaining portion of each day using a light-weight accelerometer. This will be secured to the anterior thigh of the non-affected limb using a hypoallergenic adhesive dressing (103). The ActivPAL thigh-based accelerometer differentiates sitting, standing and walking postures, which wrist-based accelerometers cannot do. The device will be fitted immediately after the baseline thigh muscle ultrasound measurement, and retrieved immediately before the post-intervention thigh muscle ultrasound measurement. Participants will then be given a wrist-based accelerometer to wear until their post-discharge 2-week follow-up appointment. This will record daily step count. The reason for switching to a wrist-based device is that the thigh-mounted device would need to have the adhesive dressing changed which would be impractical. The wrist-based accelerometer will be retrieved at the 2-week follow-up appointment. Due to limited availability of the wrist-based accelerometers, only the GPAQ will be conducted at the 3-month follow-up appointment.

		
In addition, the GPAQ will be used to estimate pre-stroke physical activity levels. This will be assessed the day after the intervention period. A higher level of physical activity pre-stroke is associated with more favourable recovery after stroke (104,105), therefore it is important to account for this confounding variable.
 
*Accelerometry and the GPAQ are not routinely used in the STH NHS acute stroke service.

Activities of daily living & physical function		
Over half of stroke survivors live with a physical disability (2). Finding optimal strategies to improve post-stroke physical function is a research priority (92). Measurement of physical function is necessary to understand the effects of the aerobic exercise intervention compared to usual care alone.
 
The Barthel Index is a simple measure of a person's ability to undertake activities of daily living and to what degree assistance is needed. This assessment is routinely used by the STH NHS acute stroke service.
 
The SPPB is short series of physical assessments that measure lower-extremity function. The test battery is designed for use in elderly and clinical populations and includes: a 3-metre walk, 5 sit-to-stand repetitions, and a set of standing balance tests.
 
The 10-metre walk test will also be used in accordance with expert recommendations for core outcome measures in stroke recovery trials (110). Instead of testing 10-metre walk speed separately to the SPPB walk speed, we will extend the SPPB 3-metre walkway by 7 metres and record the average walking speed at both distances.
 
Handgrip strength is a simple measure of upper-limb function.
 
*The Barthel Index is the only physical function assessment that the STH NHS acute stroke service use.

Acute physiological response to aerobic exercise	
 • Heart rate • Blood pressure • Oxygen saturation 
 • Cerebral blood flow (CBF) velocity 
 • Oxygen consumption ($\dot{V}O_2$) 	
Only one study has investigated the use of aerobic exercise in the acute phase of stroke (44). The only physiological variable reported was mean exercise heart rate. Collecting more in-depth physiological data will improve the mechanistic knowledge of how aerobic exercise influences cerebral perfusion and recovery from injury. Furthermore, monitoring heart rate, blood pressure and oxygen saturation in real-time will improve the safety of exercise prescription.
 
Heart rate will be measured telemetrically via a chest strap or using wireless ECG; brachial blood pressure will be measured with an oscillatory monitor; and peripheral oxygen saturation will be measured with a fingertip pulse oximeter.
 
CBF velocity is a non-invasive proxy measure of cerebral perfusion (111). Moderate-intensity aerobic exercise increases CBF velocity by 10-30% (30). Increasing blood flow to the peri-infarct area may enhance reparative processes and promote neuroplasticity (24–26,30,31,36,37,95,112). We will use a transcranial Doppler (TCD) ultrasound device to determine changes in CBF velocity measured bilaterally at the middle cerebral arteries. A specially designed, comfortable headset will be used to fix the ultrasound probes in place during exercise sessions.
 
To minimise time burden, CBF velocity will be measured a maximum of two times per participant. Both the control group and the intervention group will have resting CBF velocity measured on the second study day (t_1) and the sixth study day (t_5). For the intervention group only, we will record changes in CBF velocity throughout the exercise sessions immediately after resting measures. Measuring resting CBF velocity will enable us to understand how this variable changes in the first week of stroke under conditions of usual care and aerobic exercise training. Furthermore, as the aerobic exercise duration progresses throughout the 5-day intervention from 10 to 30 minutes, a repeated measure (first vs. fifth exercise session) will help to identify if there is a dose-response relationship between exercise duration and change in CBF velocity (intervention group only). Hypoallergenic ultrasound gel and nitrile gloves will be used. If a patient has a known allergy to ultrasound gel, this test will be excluded.
 
During moderate-intensity aerobic exercise, increased energy turnover within working muscle leads to increased $\dot{V}O_2$ and CO_2 production (30). CO_2 is a potent vasodilator and is a key regulator of CBF (30). $\dot{V}O_2$ can be used to estimate the energy expenditure of physical exercise. Combined measurement of $\dot{V}O_2$ and end-tidal CO_2 enables the estimation of the metabolic

---	---	--

	
 • End-tidal carbon dioxide (CO₂) • Mature brain-derived neurotrophic factor (mBDNF) • Platelet count • Plasma volume 	
stress and thereby intensity of exercise (61). Both $\dot{V}O_2$ and end-tidal CO₂ can be measured concurrently using an expired gas analysis system. Expired gas will be collected via a non-invasive face mask. $\dot{V}O_2$ and end-tidal CO₂ will be measured in the intervention group only during the fifth exercise session.
 
mBDNF is a key mediator of neuroprotection, neuroplasticity, memory formation and learning (28). Aerobic exercise transiently increases the systemic production and secretion of mBDNF (29). Platelets are a primary storage site of mBDNF in the blood (29). Aerobic exercise stimulates the release of platelets from the spleen which increases the circulating level of mBDNF (29,37). To accurately determine exercise-induced changes in serum mBDNF independent of platelet count, mBDNF concentration will be calculated per platelet. In addition, blood plasma contains a freely circulating pool of mBDNF that is not bound to platelets. Possible sources of plasma BDNF include the brain, skeletal muscle, peripheral blood mononuclear cells and vascular endothelial cells (29). Measurement of plasma mBDNF is necessary to determine if cellular sources of BDNF are secreted into circulation during exercise. However, during moderate-intensity exercise, water shifts from plasma into both the interstitial and intracellular fluid compartments of contracting skeletal muscle. Thus it is important to correct for changes in plasma volume to prevent erroneous interpretations of changes in mBDNF concentration (113). In sum, by assessing changes in the total mBDNF system (serum, volume-corrected plasma, platelets, and mBDNF per platelet), it is possible to quantify cellular sources of denovo mBDNF, and to differentiate this from changes in mBDNF that result from altered blood plasma volume and movement of mBDNF between plasma and platelet pools (29).
 
Due to the invasive nature of venous blood sampling and the expense of analysing mBDNF, we have chosen to limit blood sample collection to a maximum of two timepoints per participant at t_5: 1) baseline (both groups), and 2) post-exercise (intervention group only). We have chosen to measure mBDNF at the fifth aerobic exercise session which is 30 minutes in duration. This exercise duration has consistently been shown to increase circulating mBDNF (29). Hypoallergenic nitrile gloves, dressings and plasters will be used.

--	--	---

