7.3. Sample size

A minimum of 24 participants (12 per arm) will be recruited. 12 has been recommended as a minimum number of participants per arm to be recruited for a clinical trial where there is no prior information to guide sample size (60). This figure is suggested to represent the lower threshold required to estimate the standard deviation of measures with adequate precision (60). Adjusting for a predicted 20% attrition rate, the target sample size is 30.

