7.9. Blinding

It is not possible to blind participants or on-site research team members to group allocation. Statistical analyses will be conducted by an independent research team member who is blinded to group allocation.

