Thigh accelerometer removed														✓	✓			
Physical function (SPPB, 10-m walk, handgrip strength)		✓	✓											✓	✓		✓	✓
Activities of daily living (Barthel Index)		✓	✓											✓	✓	✓	✓	✓
Disability (mRS)		✓	✓											✓	✓		✓	✓
Acute fatigue (RoFS)		✓	✓		✓			✓			✓		✓	✓	✓		✓	✓
Cognitive function (MoCA)		✓	✓														✓	✓
Chronic fatigue (FSS)		✓	✓														✓	✓
Pre-morbid physical activity levels (GPAQ)														✓	✓			
Anxiety and depression (GAD-7, PHQ-9)		✓	✓														✓	✓
Optimism (rLOT)		✓	✓														✓	✓
Health-related quality of life (EQ-5D)		✓	✓														✓	✓
Exercise self-efficacy		✓	✓											✓	✓		✓	✓
Wrist accelerometer fitted														✓	✓			
Post-discharge physical activity (wrist accelerometer returned)														✓	✓			

	Study period																	
	Enrolment	Allocation	Post-allocation															
Post-stroke timeline	24-72 h (study starts)				≥48 h; 5-day intervention								+1 day	Follow-up				
	+2 weeks			+3 months (study ends)										t ₇		t ₈		
Study timeline	t ₋₁	t ₀		t ₁		t ₂		t ₃		t ₄		t ₅		t ₆		t ₇		
	Group →	C	I	C	I	C	I	C	I	C	I	C	I	C	I	C	I	
Post-discharge physical activity (GPAQ)																	✓	✓
Resting cerebral blood flow velocity (transcranial Doppler ultrasound)					✓	✓							✓	✓				
Resting mature brain-derived neurotrophic factor													✓	✓				
Serious/adverse events			✓	✓	✓	✓	✓	✓	✓	✓	✓	✓	✓	✓	✓	✓	✓	✓
Length of stay														✓	✓	✓	✓	
Qualitative interviews														✓	✓		✓	✓
Aerobic exercise-specific investigations:																		
Δ heart rate (telemetry or ECG)						✓		✓		✓		✓		✓				
Δ blood pressure (oscillometry)						✓		✓		✓		✓		✓				
Δ perceived exertion (RPE scale)						✓		✓		✓		✓		✓				
Δ oxygen saturation (pulse oximeter)						✓		✓		✓		✓		✓				
Δ cerebral blood flow velocity (transcranial Doppler ultrasound)						✓							✓					
Δ mature brain-derived neurotrophic factor													✓					
Δ end-tidal CO ₂ and $\dot{V}O_2$													✓					

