Recruitment rate	Number of participants recruited per month of the recruitment period.
Exclusion rate	Number of ineligible patients divided by the total number of patients admitted to the RHH stroke service during the recruitment period.
Consent rate	Percentage of eligible patients who consent to participate.
Dropout rate	Percentage of individuals that discontinue participation after the study has commenced. Voluntary reasons for dropout will be recorded. Early discharge from hospital will not count as a dropout.
Participant fidelity	Completion of key exercise components in accordance with the exercise protocol including: percentage of planned exercise session duration completed, percentage of target exercise intensity per session attained, and percentage of total planned exercise sessions completed.
Completeness of data	Percentage of planned measurements completed and recorded.
Safety	Number of SAE and AEs related to the intervention.
Acceptability of intervention (participant interview)	Comfort and ease of using cycling apparatus.
Acceptability of study procedures (healthcare professional interview)	
 • Attitudes towards the intervention • Burden on staff and participants • Perceived effectiveness of the intervention

12. Intervention

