
The day after completing the first exercise bout, participants will undertake a single aerobic exercise session per day for 4 days (5 exercise sessions in total). If patients are discharged earlier, study participation will terminate on the day of discharge. The workload that elicited an RPE of 13 at the start of the conditioning phase in the first aerobic exercise session will be used to guide the initial workload for the conditioning phase in subsequent sessions.

Number of repetitions (rpm multiplied by minutes) completed during the warm-up,

conditioning phase and cool-down will be included within therapy dose calculations. Verbal communication provided by the operator will be standardised (detailed in Table 6, Appendix).

Through consultations with stroke survivors and healthcare practitioners we acknowledge the need for a flexible exercise protocol. It was expressed to us that patients' level of fatigue and physical function may fluctuate throughout the duration of hospital stay depending on various intrinsic and extrinsic factors. Thus, the workload used for each exercise session will be a collaborative choice made between the researcher and the participant.

[figure not shown]

Figure 5. Schematic diagram of 5-day exercise protocol.

Note: Blue = passive cycling (no exertion) = 5 minutes; brown = warm up/cool down; pink = active cycling (moderate intensity). Active cycling duration = 5 minutes per bout. Passive recovery intervals = 1 minute (blue).

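### Pre-stroke physical activity, which the protocol wants to account for, is asked only after the intervention, when the arm is known; it should be asked at baseline before allocation is revealed

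*Protocol*

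**What the plan says.** The physical activity entry of Table 4 (Protocol 9.2) states that "the GPAQ will be used to estimate pre-stroke physical activity levels". It links higher pre-stroke activity with better recovery and concludes "therefore it is important to account for this confounding variable". The timing is given in words: "This will be assessed the day after the intervention period". Table 3 agrees. The pre-morbid GPAQ row has one pair of ticks, in the same position as removal of the thigh accelerometer (t6), and none at t0. The FSS, GAD-7, PHQ-9, rLOT, EQ-5D and exercise self-efficacy scale are all ticked at t0. The GPAQ at 3 months is a separate measure of activity after discharge.

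Three other places bear on the point:

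- Section 7.9: "It is not possible to blind participants or on-site research team members to group allocation". Only the analyst is blinded.
- Section 12.3.3: "If patients are discharged earlier, study participation will terminate on the day of discharge".
- Table 6 (section 11), under dropout rate: "Early discharge from hospital will not count as a dropout".

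**The concern.** A covariate meant to describe participants before treatment is safest when recorded before anyone knows the treatment. Pre-stroke activity is a fixed historical quantity, so nothing in its nature requires waiting until t6, and the protocol gives no reason for the delay. By t6 one arm has been offered five supervised exercise sessions. The questionnaire then asks that arm how active it used to be, with participant and staff aware of the allocation. Table 4 itself expects that the intervention may raise exercise self-efficacy and may alter optimism, so a difference between arms in how past exercise is reported is plausible, though not shown.

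What is at stake is objective 4a, the between-arm effect signal used to help choose the primary outcome of a definitive trial. If reported pre-stroke activity differs between arms because of reporting, adjusting for it moves the effect estimate for a spurious reason, and a baseline table that includes it can suggest an imbalance that was never there or hide a real one. An analysis plan cannot recover a pre-allocation answer that was not collected.

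**Working it through.** **The plan's own figure.** Section 7.3 states "A minimum of 24 participants (12 per arm) will be recruited" and allows for 20% attrition: 24 / (1 − 0.20) = 30. This reproduces the target. The point does not depend on it; it only supplies the arm sizes used below.

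**Timing.** Allocation is at t0, the sessions run from t1 to t5, and the pre-stroke GPAQ is at t6. Tables 3 and 4 agree, and no earlier collection is scheduled. Table 5 covers only the post-discharge GPAQ. Every pre-stroke GPAQ answer is therefore given after allocation and after the intervention period.

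**Possible effect on an adjusted estimate (assumed inputs).** In a linear model with a covariate,

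adjusted effect = difference in outcome means − b × difference in covariate means,

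where b is the within-arm slope of the outcome on the covariate. If reporting alone adds a difference s between arms, the adjusted effect moves by −b × s. Neither s nor b is in the documents. With s from 0.2 to 0.5 SD and b from 0.3 to 0.5 SD per SD:

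- smallest shift: 0.2 × 0.3 = 0.06 SD
- largest shift: 0.5 × 0.5 = 0.25 SD

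The standard error of a standardised mean difference with 12 per arm is √(2/12) = 0.41 SD, so the illustrated shift is 0.06/0.41 = 0.15 to 0.25/0.41 = 0.61 of one standard error. Without adjustment for this variable the shift is zero.

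**Why a clean baseline value is useful.** Under randomisation, the chance that a standardised covariate differs between arms by more than 0.5 SD (normal approximation) is about 22% with 12 per arm, and about 17% with 15 per arm (standard error √(2/15) = 0.37 SD). A difference seen at t6 could be such a chance imbalance or a reporting effect, and the data could not tell them apart.

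**Early discharge (assumed rates; the protocol gives none).** If all 30 are randomised and each is discharged before t6 independently with the rate shown:

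| Assumed early-discharge rate | Expected number with pre-stroke GPAQ | Chance of fewer than 24 |
|---|---|---|
| 10% | 27 | 3% |
| 20% | 24 | 39% |
| 30% | 21 | 84% |
| 40% | 18 | 98% |

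These figures count the covariate only. If participation ends at discharge, as section 12.3.3 says when read literally, the t6, 2-week and 3-month outcomes go too, and the missing GPAQ costs an adjusted analysis nothing further. If follow-up continues, as the dropout definition in Table 6 may imply, outcomes would exist without the covariate, and the dropout rate as defined would not show the gap.

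**The case against.** The strongest reply is that the harm depends on an analysis the protocol does not specify. Objective 4a describes the effect signal as a difference between group means and mentions no adjustment; accounting for a variable could mean no more than describing it. This stands: the bias is conditional. It does not remove the point, because describing balance also relies on an answer unaffected by allocation, and the timing is fixed in this document.

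A reader might infer that the intervention alters the covariate itself. The documents do not support that. Pre-stroke activity is fixed before randomisation; only its recall or reporting can vary by arm, and nothing shows that it does or in which direction.

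A reader might also infer that each early discharge removes a participant from an adjusted analysis because of the GPAQ's timing. That is not supported either. On the literal reading of section 12.3.3 the outcomes are lost as well, so an earlier GPAQ would rescue nobody. The claim needs continued follow-up, which the protocol leaves unclear.

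Strictly, a prognostic variable in a randomised trial is not a confounder; that label is the protocol's own.

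Finally, t0 is already a full visit 24 to 72 hours after stroke, and the protocol names patient burden and fatigue as considerations. That is a real cost. The protocol does not give it as the reason for t6, and the visit already includes several questionnaires.

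**Conclusion.** The point holds as a minor one. The only measurement of pre-stroke activity comes after allocation and after the intervention, in unblinded participants, although the protocol wants to account for it. Differential reporting is possible and its size unknown; the 0.06 to 0.25 SD range rests wholly on assumed inputs and is below the 0.41 SD standard error even at its upper end. It matters only if the variable is used for adjustment or to judge balance, and then only for the exploratory signal of Aim 4. The primary feasibility aim does not depend on the value of this variable, and no figure in the plan changes. The loss through early discharge is a conditional, secondary consequence.

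**What to change.** In Table 3, move the pre-morbid GPAQ row from t6 to t0. In Table 4, change the timing sentence to match and state that the questionnaire is completed before allocation is revealed. The order has to be written down because Table 3 also places allocation at t0, so moving the row is not enough by itself. The 3-month GPAQ stays as it is.

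Separately, reconcile section 12.3.3 with the dropout definition in Table 6, so that it is clear whether outcomes are still collected after an early discharge.

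The cost is a few more minutes at a full baseline visit, offset by the same minutes saved at t6. Sample size and the other assessments are unaffected.
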